**LABORATORY PARAMETERS**

PARAMETER	GRADE 1 MILD	GRADE 2 MODERATE	GRADE 3 SEVERE	GRADE 4 EXTREME
HAEMATOLOGY				
Haemoglobin (g/L) Female	113 – 110	109 – 95	94 – 80	< 80
Haemoglobin (g/L) Female (change from baseline)	Any decrease – 15	16 – 20	21 – 50	> 50
Haemoglobin (g/L) Male	129 – 125	124 – 105	104 – 85	< 85
Haemoglobin (g/L) Male (change from baseline)	Any decrease – 15	16 – 20	21 – 50	> 50
White Blood Count (x10^9/L) Increase	11.5 – 15.0 OR 3.5 – 2.5	15.1 – 20.0 OR 2.4 – 1.5	20.1 – 29.9 OR 1.4 – 1.0	≥ 30.0 OR < 1.0
Absolute Neutrophils (x10^9/L)	1.9 – 1.5	1.4 – 1.0	0.9 – 0.5	< 0.5
Lymphocytes (x10^9/L)	1.0 – 0.8	0.7 – 0.5	0.4 – 0.2	< 0.2
Platelets (x10^9/L)	129 – 125	124 – 100	99 – 25	< 25
BIOCHEMISTRY				
ALT (increase by factor)	1.1 – 2.5 x ULN	2.6 – 5.0 x ULN	5.1 – 10.0 x ULN	> 10.0 x ULN
Alkaline Phosphatase (increase by factor)	1.1 – 2.0 x ULN	2.1 – 3.0 x ULN	3.1 – 10.0 x ULN	> 10.0 x ULN
Bilirubin (increase by factor)	1.1 – 1.5 x ULN	1.6 – 2.0 x ULN	2.1 – 3.0 x ULN	> 3.0 x ULN
Creatinine (increase by factor)	1.1 – 1.5 x ULN	1.6 – 3.0 ULN	> 3.0 ULN	Dialysis

Clinical Protocol: CRC374/Ad4HIV

Statistical Analysis Plan

Role	Signature	Date
[name] (Senior Medical Statistician, Surrey CTU) Author		20 July 2021
[name] Imperial College London Principal Investigator		27 July 2021
[name] Director of Surrey Clinical Trials Unit		20-JUL-2021
Any other sponsor Representatives	N/A	N/A

Version Control Log

Version No.	Page No.	Section	Change Details
0.1	Various	Various	Initial version.
0.2	Various	Various	After initial review by other team members
0.3	Various	Various	After meeting with investigators, Primary endpoint was changed to nasal mucosal secretion

Table of Contents

1	Abbreviations	5
2	Study Rationale	6
3	Study Design	6
3.1	Part 1	6
3.2	Part 2	7
4	Vaccination Schedule – Part 1 & Part 2	8
5	Randomisation	9
5.1	Part 1	9
5.2	Part 2	9
6	Blinding	9
7	Replacing Withdrawals	10
8	Study hypothesis	10
9	Study Populations	10
10	Study Endpoints	10
10.1	Primary Endpoints Measure(s) - Part 1 & Part 2	10
10.1.1	Immunogenicity	10
10.1.2	Safety and Tolerability	10
10.2	Secondary Endpoints Measure(s) – Part 1 & Part 2	11
10.2.1	Immunogenicity:	11
10.3	Exploratory Endpoints Measure(s) - Part 1 & Part 2	11
11	Data Transfers	11
12	Statistical Analysis	12
12.1	Responders	12
12.2	Primary Endpoint Analysis	12
12.2.1	Assessing Immunogenicity	12
12.2.2	Safety and Tolerability	14
12.3	Secondary Endpoint Analysis	15
12.4	Exploratory Endpoint Analysis	15
13	Summary Statistics	15
14	Multiplicity	16
15	Missing data	16
16	Interim analysis	16
17	Statistical software	16

18	List of Tables	16
----	----------------------	----

1 Abbreviations

Ab	Antibodies
CTU	Clinical Trials Unit
ELISA	Enzyme Linked Immunosorbent Assay
HIV	Human immunodeficiency virus
IMP	Investigational Medical Product
LAP	Lab Analysis Plan

2 Study Rationale

This study aims to evaluate the use of new HIV-1 vaccine products in a phase I clinical trial by exploring the impact of different boosting options for MVA-C and CN54gp140 for oral Ad4 serotype 4 vector prime expressing HIV-1 CN54 (Ad4-EnvCN54) to optimise systemic and mucosal responses.

This regime will identify the most immunogenic strategy for the induction of durable mucosal and systemic protective antibody responses. This will facilitate up-selection of the most promising regime for accelerated development towards a phase II efficacy trial.

Part 1 is exploratory and designed to select conditions capable of promoting enhanced systemic and mucosal B cell responses in a limited number of participants.

Part 2 is dependent upon Part 1 and is designed to study groups selected on performance in part 1 in an expanded number of subjects. Data from both stages will be combined for safety and immunological analyses.

3 Study Design

To identify an effective Ad4 based oral vaccine that promotes systemic and mucosal responses to the HIV-1 envelope glycoprotein. This study will adopt a two-part adaptive clinical trial.

The study will assist in rapidly screening the impact of different routes, combination regimes and boosting options to Ad4-EnvCN54, MVA-CN54 and CN54gp140 / MPLA, to augment systemic and mucosal antibody responses following initial priming with Ad4.

This is a phase I trial in healthy male and female participants. The study will enrol 48 participants to Part 1 (6 in each group) and 12 participants in Part 2. Recruitment will select potential participants who are willing to undergo serial blood draws. Additional participants may be enrolled to replace any early withdrawals.

The clinical trial was conducted at the NIHR Imperial Clinical Research Facility (ICRF) at Hammersmith Hospital, London.

3.1 Part 1

In Part 1, n=6 participants per group will be randomised to groups A-H (Table 1). This design varies the number of Ad4 administrations, from 1 to 3, combined with either CN54gp140 protein boosts (A-D) or co-administration of gp140 with MVA (E-H).

Arm 1 (Groups A-D): Depending on the allocation of groups, participants will receive Ad4-EnvCN54 or placebo orally, CN54gp140/MPLA, and placebo I.M injections at month 0 (Week 0), 3 (Week 12) & 6 (Week 24).

Arm 2 (Groups E-H): Depending on the allocation of groups, participants will receive Ad4-EnvCN54 or placebo orally, CN54gp140/MPLA and MVA-CN54 I.M injections at month 0 (Week 0), 3 (Week 12) & 6 (Week 24).

Groups A (gp140 alone) and E (MVA-CN54/CN54gp140 alone) will serve as control groups to assess the added benefit of the Ad4 vector. Each vaccine group (A-H) will be assessed for number of mucosal responders (mucosal antibody (nasal/rectal/genital) as measured by ELISA), and titre (mucosal and systemic) of antigen specific binding antibody.

Enrolment through to completion of the primary immunological assessment for each group will be 7 months.

3.2 Part 2

The study will enrol an additional 6 participants to two groups in Part 2 (Table 2). The best regimes from groups A-D (Ad4-EnvCN54 /CN54 rgp140) and/or E-H (Ad4-EnvCN54/MVA-CN54/CN54 rgp140) (if meeting the pass criteria) will be expanded to n=12.

The pass criteria for mucosal responders will be analysed in the first 32 participants (first four participants from each dosing group) at week 26 (the primary immunogenicity endpoint). The primary pass criteria will assess IgA responses in rectal mucosal samples, whereby a group will be considered to have met the pass criteria if there is a mucosal IgA titre greater than 100 ng/mL in the rectal secretions of ≥2 participants within a group at week 26.

However, if none of the groups meet this criterion, the selection will be expanded to include IgA responses from other mucosal secretions (nasal, cervico-vaginal (female participants) and semen (male participants)).

In the event that none/more than one of the groups meet this criterion, the selection will be based on week 26 median serum IgG titres. Statistical analysis comparing across groups A-D and E-H will be performed using the Kruskal-Wallis Test with Dunn's correction for multiple comparisons.

In the event that there is no statistical significance observed, the vaccination groups with the least and greatest exposure to the vaccine products (A and D) will be expanded into part 2 to allow for greater assessment of safety data.

4 Vaccination Schedule – Part 1 & Part 2

The doses, methods and schedule of immunisation are described below.

Table 1: Schedule of Doses and Method of Vaccinations

PART I							PART II	
	Group	N	Month 0	Month 3	Month 6		N	Vaccinations 1,2,&3
ARM 1	A	6	Oral placebo	CN54gp140 + Oral placebo +I.M placebo	CN54gp140 + Oral placebo +I.M placebo		12	Selected dosage from Part I
	B	6	Ad4-EnvCN54	CN54gp140 + Oral placebo +I.M placebo	CN54gp140 + Oral placebo +I.M placebo			
	C	6	Ad4-EnvCN54	CN54gp140 + Ad4-EnvCN54 +I.M placebo	CN54gp140 + Oral placebo +I.M placebo			
	D	6	Ad4-EnvCN54	CN54gp140 + Ad4-EnvCN54 +I.M placebo	CN54gp140 + Ad4-EnvCN54 +I.M placebo			
ARM 2	E	6	Oral placebo	CN54gp140 + MVA-CN54 + Oral placebo	CN54gp140 + MVA-CN54 + Oral placebo			
	F	6	Ad4-EnvCN54	CN54gp140 + MVA-CN54 + Oral placebo	CN54gp140 + MVA-CN54 + Oral placebo			
	G	6	Ad4-EnvCN54	CN54gp140 + MVA-CN54 + Ad4-EnvCN54	CN54gp140 + MVA-CN54 + Oral placebo			
	H	6	Ad4-EnvCN54	CN54gp140 + MVA-CN54 + Ad4-EnvCN54	CN54gp140 + MVA-CN54 + Ad4-EnvCN54			
		48					max 12	

5 Randomisation

5.1 Part 1

The study will use sentinel dosing as a safety precaution. The first 6 participants successfully enrolled into the trial will be sequentially pre-allocated to treatment groups B, C, D, F, G and H. The first participant will be enrolled to group B. The safety data for this participant will be reviewed at day 7 before enrolling the next participant to group C. This process will be repeated for the other groups. This will ensure an escalation of the number of Ad4-EnvCN54 administrations combined with either CN54gp140 protein boosts (B-D) or co-administered CN54gp140 and MVA-CN54 (F-H).

After the accumulated safety data (up to day 7) for the 6th participant has been reviewed, on their first day of dosing the remaining participants will be block randomised into groups as follows:

- Block 1 (n=10): A, A, B, C, D, E, E, F, G, H
- Blocks 2-5 (n=8/block): A, B, C, D, E, F, G, H

5.2 Part 2

Participants will be randomised to the groups chosen for expansion. Participants will be blind to the vaccine regime group to which they have been assigned. The laboratory undertaking immunological analysis will also be blinded to group and dosing regimen to prevent bias in analysis.

Six additional healthy participants per group will be recruited and randomised to the best two regimes from A-D (Ad4-EnvCN54/CN54gp140) and E-H (Ad4-EnvCN54/MVACN54/CN54gp140).

The visits schedule for participants in Part 2 will be the same as that for participants in Part 1.

6 Blinding

This is a single-blind, randomised trial with placebo controls. Participants will be block-randomised centrally, using the randomisation schedule produced by the statisticians at the Surrey CTU, to the study groups shown in Table 1, using a computer-generated algorithm with a back-up manual procedure. Randomisation will be stratified on the basis of gender.

All participants in Part 1 and Part 2 will be blinded to the vaccine regime group to which they have been assigned. The laboratory teams undertaking immunological analysis will also be blinded to group and dosing regimen to prevent bias in analysis. The clinical team will remain unblinded to the vaccine regime of trial participants throughout.

7 Replacing Withdrawals

As the number of participants per group is small and hence each participant is essential to the study, those who withdraw from the study will be replaced before completion of the week 26 visit.

8 Study hypothesis

The study hypothesis is that priming with an orally delivered mucosal replicating vector (Ad4) will significantly enhance the magnitude and durability of mucosal and systemic antibody responses to HIV-1 gp140 on boosting with recombinant protein, with or without co-administration of a non-replicating pox vector (MVA-C).

9 Study Populations

Four different study populations have been defined and listed according to their importance.

1. Safety population

Those participants who received at least one dose of experimental vaccine will be included in the safety population

2. Per-protocol (PP) population:

PP includes all participants randomised and immunised with all scheduled vaccinations, and who completed the trial with no major protocol deviations

3. Intention-to-treat (ITT) population:

ITT population includes all participants randomised and given at least one vaccination in the trial

4. Modified-Intention-to-treat (mITT):

mITT population includes all participants randomised and given at least one immunisation in the trial (including those participants whose sample collection occurred outside the allowed windows)

10 Study Endpoints

10.1 Primary Endpoints Measure(s) - Part 1 & Part 2

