Group	N	Month 0	Month 3	Month 6																																					
A	6	Oral placebo	CN54gp140 +Oral placebo +I.M placebo	CN54gp140 +Oral placebo +I.M placebo																																					
B	6	Ad4-EnvCN54	CN54gp140 +Oral placebo +I.M placebo	CN54gp140 +Oral placebo +I.M placebo																																					
C	6	Ad4-EnvCN54	CN54gp140 + Ad4-EnvCN54 + I.M placebo	CN54gp140 +Oral placebo + I.M placebo																																					
D	6	Ad4-EnvCN54	CN54gp140 + Ad4-EnvCN54 +I.M placebo	CN54gp140 + Ad4-EnvCN54 +I.M placebo																																					
E	6	Oral placebo	CN54gp140 +MVA-CN54 +Oral placebo	CN54gp140 +MVA-CN54 +Oral placebo																																					
F	6	Ad4-EnvCN54	CN54gp140 +MVA-CN54 +Oral placebo	CN54gp140 +MVA-CN54 +Oral placebo																																					
G	6	Ad4-EnvCN54	CN54gp140 +MVA-CN54	CN54gp140 +MVA-CN54																																					

			+ Ad4-EnvCN54	+Oral placebo
H	6	Ad4-EnvCN54	CN54gp140 +MVA-CN54 + Ad4-EnvCN54	CN54gp140 +MVA-CN54 + Ad4-EnvCN54
	48			

Participants will be randomised for recruitment into groups A-H in Part 1. The number of Ad4-EnvCN54 administrations combined with either gp140 protein boosts (A-D) or co-administration of gp140 with MVA-CN54 (E-H) will vary. Groups A (CN54gp140 alone) and E (MVA-CN54/CN54gp140 alone) will serve as control groups to assess the added benefit of the Ad4 vector. Following completion of Part 1, each vaccine group (A-H) will be assessed for number of mucosal responders (mucosal antibody (rectal/genital/oral) as measured by ELISA), and titre (mucosal and systemic) of antigen specific binding antibody. The primary immunogenicity endpoint will be Week 26; Visit 9. The vaccine groups and regimes (one from B-D and one from F-H) that have the best positive response at this timepoint will be expanded in Part 2 of the study.

Based on data from the MUCOVAC2 study, in which participants received 3 intramuscular doses of CN54gp140 with GLA-AF adjuvant, we anticipate that there will be no mucosal responders in group A (although there will be detectable systemic IgG responses). Enrollment through to completion of the primary immunological assessment for each group will be 7 months.

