**Vaccine Schedule for Part 2**

The study will enrol an additional 12 participants to Part 2. The best regimes from A-D (Ad4-EnvCN54 / CN54gp140) and F-H (Ad4-EnvCN54 / MVA-CN54 / CN54gp140) will be expanded to n=12. Immunogenicity data will be analysed in 32 participants at week 26 (Primary Immunogenicity Endpoint). The study design for Part 2 will be the same as that used for Part 1 (Table 1: Vaccine and Immunisation Schedule) for the best responding groups only.

Selection will be based on total number of responders. In the event that more than one group has the same number of responders, mucosal antibody titre will be used to rank groups to determine which to take forward to Part 2. Should mucosal titers be indistinguishable between groups, then serum antibody levels will be taken into consideration in the selection of groups to progress to Part 2. The criterion for a positive mucosal response, and methods for ranking groups on the basis of mucosal and serum antibody titers, will be specified in the Laboratory Analysis Plan (LAP). If any group is associated with unacceptable product related adverse events, it will be discontinued from further study.

The decision to progress any group to Part 2 will be taken by the Trial Management Group.

Summary	Summary Details
----------------	------------------------

Information Type																												
Formulations	
 
Ad4-EnvCN54 at the dosage of <math>10^{10}</math> VP will be administered orally
 
MVA-CN54 at the dosage of <math>1.0 \times 10^8</math> TCID50 will be administered by IM needle injection
 
CN54gp140 at the dosage of 100<math>\mu</math>g will be administered with 5<math>\mu</math>g of MPLA in a liposomal formulation and administered by IM needle injection
 
Placebo 1: Capsule administered orally
 
Placebo 2: Buffered saline administered by I.M needle injection
 
																											

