### 14.3 SAMPLE SIZE

It is not the remit of this Phase I trial to recruit a sufficient number of participants to be statistically confident about the differences between groups. By the end of this study 6 participants will have been exposed to each schedule in Part 1 (groups A – H) and this provides confidence around the response/event proportions of 0–100% in Table 7.

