**Table 7: Sample Size**

Number of “responders”	Proportion if n=6	95% confidence interval 
0	0%	0 – 39%
1	17%	0 – 64%
2	33%	4 – 78%
3	50%	12 – 88%
4	67%	22 – 96%
5	83%	36 – 100%
6	100%	54 – 100%

 Clopper-Pearson method (suitable for small sample sizes)

It is difficult to give an estimate of the power of group comparisons using quantitative antibody titre outcomes at this stage as this is dependent on the number of responders.

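### Table 7's interval for zero of six should be 0–46%, not 0–39%, and the documents do not settle whether Part 2 selection rests on four or six participants per group

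*SAP*

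**What the plan says.** **Precision.** Protocol section 14.3 says "By the end of this study 6 participants will have been exposed to each schedule in Part 1" and that "this provides confidence around the response/event proportions of 0–100% in Table 7". Table 7 lists 95% intervals for 0 to 6 responders out of six. Its footnote names the "Clopper-Pearson method (suitable for small sample sizes") and no other method. The 0/6 row reads 0–39%; the 6/6 row reads 54–100%.

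**Data used for selection.** SAP section 3 sets the sizes: "The study will enrol 48 participants to Part 1 (6 in each group) and 12 participants in Part 2". On which of these participants decide the Part 2 groups, the documents say:

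- SAP section 3.2: "The pass criteria for mucosal responders will be analysed in the first 32 participants (first four participants from each dosing group) at week 26".
- Protocol section 2, Vaccine Schedule for Part 2: "Immunogenicity data will be analysed in 32 participants at week 26 (Primary Immunogenicity Endpoint").
- Protocol section 2, Study Design: "Following completion of Part 1, each vaccine group (A-H) will be assessed for number of mucosal responders", with the best groups then expanded.

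Protocol sections 7.6 and 10.1.3 describe the selection without giving an n.

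**The rule.** Under SAP section 3.2 a group passes if at least two of its participants exceed a rectal IgA threshold at Week 26. If no group passes, other secretions are considered. If none or more than one passes, selection moves to serum IgG, "performed using the Kruskal-Wallis Test with Dunn's correction for multiple comparisons", within A–D and within E–H. If nothing is significant, a default expansion of groups A and D applies. No n is given for the serum step.

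**The concern.** Two things look wrong.

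First, the 0/6 limit does not match the rest of Table 7. Zero is a likely count here. The protocol expects no mucosal responders in group A, and the primary safety endpoints (Grade 3–4 reactions, vaccine-related SAEs) may well show zero in a group of six. A reader using the table would take a true rate above 39% as excluded when the stated method excludes only rates above 46%.

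Second, the same decision is described on two data sets: 32 participants, or all of Part 1. Choosing regimens is what Part 1 is for. If the choice rests on four per group, readers need the precision at four, and they need to know whether the other 16 participants play any part. Neither is given.

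**Working it through.** **1. Reproducing Table 7.** For x of n, the two-sided 95% Clopper-Pearson limits are the 2.5% quantile of Beta(x, n−x+1) and the 97.5% quantile of Beta(x+1, n−x). The lower limit is 0 when x=0 and the upper limit is 100% when x=n.

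| x of 6 | Table 7 | Recomputed, two-sided |
|---|---|---|
| 0 | 0–39% | 0–45.9% |
| 1 | 0–64% | 0.4–64.1% |
| 2 | 4–78% | 4.3–77.7% |
| 3 | 12–88% | 11.8–88.2% |
| 4 | 22–96% | 22.3–95.7% |
| 5 | 36–100% | 35.9–99.6% |
| 6 | 54–100% | 54.1–100% |

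Six rows reproduce; the first does not. The two-sided upper limit for 0/6 is 1 − 0.025^(1/6) = 45.9%. The printed 39% is 1 − 0.05^(1/6) = 39.3%, the one-sided limit. The table shows this itself: 6/6 mirrors 0/6, and 100 − 54 = 46.

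**2. Data for the selection.** 8 groups × 4 = 32. The remainder is 48 − 32 = 16, and 16/48 = 33%.

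**3. Precision at n=4 (same formula).** 0/4: 0–60%; 1/4: 1–81%; 2/4: 7–93%; 3/4: 19–99%; 4/4: 40–100%.

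**4. The threshold of two.** 2/4 = 50%; 2/6 = 33%. The chance that a group with true rate p passes is 1 − (1−p)^n − np(1−p)^(n−1). The documents give no rates, so these are assumed:

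| p | n=4 | n=6 |
|---|---|---|
| 0.2 | 18.1% | 34.5% |
| 0.3 | 34.8% | 58.0% |
| 0.5 | 68.8% | 89.1% |
| 0.6 | 82.1% | 95.9% |

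With three groups at 0.3, 0.3 and 0.6, the chance that only the best passes is 0.821 × (1 − 0.348)² = 35% at n=4 and 0.959 × (1 − 0.580)² = 17% at n=6. An unchanged threshold of two is therefore an easier rule at six.

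**5. Serum step, if run at n=4 (assumed).** Further assumptions: four groups, normal log titres, one group shifted, 5% level, chi-square approximation for Kruskal-Wallis. Simulated power:

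| Shift | n=4 | n=6 |
|---|---|---|
| 1.5 SD | about 30% | about 59% |
| 2 SD | about 54% | about 85% |

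Now take complete separation, with the better group above every other value and the other three at equal mean ranks. This arrangement gives the smallest H that complete separation allows.

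- n=4: H = 12/(16×17) × 4 × [(14.5−8.5)² + 3(6.5−8.5)²] = 8.47 on 3 df, p = 0.037.
- n=6: H = 12/(24×25) × 6 × [(21.5−12.5)² + 3(9.5−12.5)²] = 12.96, p = 0.005.

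The omnibus test is therefore significant at either n. Dunn, with an assumed Bonferroni factor of 6, uses z = difference in mean ranks / √[N(N+1)/12 × 2/n].

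- n=4: 8/3.367 = 2.38, adjusted p = 0.105.
- n=6: 12/4.082 = 2.94, adjusted p = 0.020.

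Over random arrangements of the other three groups, at least one Dunn comparison for the better group is significant in about 77% of cases at n=4 and in all at n=6.

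**The case against.** **On Table 7.** Some statisticians put the whole 5% in one tail when the count is zero. That does not rescue the row: the same convention would give 6/6 a lower limit of 0.05^(1/6) = 61%, and the table prints 54%. It is fair, however, that section 14.3 ties Table 7 to exposure by the end of Part 1, not to the selection look. The table is not misapplied to four per group; precision at four is simply not given.

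**On the early look.** The SAP and one protocol passage agree on 32. The design is adaptive and meant for rapid screening, and section 14.3 disclaims confidence about group differences. The SAP's final analyses use six per group in Part 1 and 12 in Part 2. Looking early is a legitimate choice, and this part of the objection stands.

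A reader might infer more than the documents support:

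- **That selection must wait for all 48.** Waiting would delay Part 2 by the time needed to enrol 16 people: 2 to 4 months at an assumed 8 to 4 per month. With the threshold left at two, it would also lower the bar, as step 4 shows.
- **That at n=4 a clearly better regimen would often fall to the default.** Under complete separation Kruskal-Wallis is always significant. The 77% concerns Dunn comparisons only.
- **That the serum step is run at n=4.** This is the natural reading, but the restriction to 32 is attached to the mucosal pass criteria.
- **That the first 32 enrolled are exactly four per group.** Six sentinels, a block of 10 and two blocks of 8 do sum to 32, but randomisation is stratified by gender and withdrawals are replaced, so this need not hold.

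**Conclusion.** The 0/6 row of Table 7 is wrong as written. The two-sided interval is 0–46%, so the printed upper limit is about 7 percentage points too low. This needs no assumption beyond the method the table names.

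The protocol is inconsistent with itself, and in part with the SAP, on whether selection uses 32 participants or follows completion of Part 1. The precision at four per group is missing: 0–60% for 0/4 and 7–93% for 2/4.

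The cost to the serum step depends on n=4 and on the assumed shifts. Under those assumptions Kruskal-Wallis power roughly halves at 1.5 SD (about 30% against 59%) and falls from about 85% to 54% at 2 SD. That is a reason to state n and to check the selection on the full data. It does not show that the early look is an error. The effect is confined to the choice of groups for Part 2.

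**What to change.** 1. In Table 7, change the 0/6 interval to 0–46%. If the protocol is no longer being amended, carry the corrected value into the SAP or study report.
2. Reconcile the two statements in protocol section 2 with SAP section 3.2, so that one data set is named for the selection. State n for the serum IgG step, and preferably whether the absence of significance is judged on Kruskal-Wallis or on the Dunn comparisons.
3. If the early look is kept, state that selection rests on four per group and add the n=4 intervals from step 3. Repeat the selection rule on all 48 once Week 26 is complete, and report whether the same groups would have been chosen.
4. State how the threshold of at least two participants carries over to six in that repeat. A count of two and a proportion of 50% are different rules, and the choice should be written down before the repeat is run.

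No extra participants, visits or samples are needed, because the other 16 are sampled at Week 26 anyway. The cost is wording, one repeat analysis and a slightly less favourable stated interval. The SAP was signed in July 2021 and describes the trial's conduct at its site in the past tense, so the selection may already have been made; all four changes remain possible in that case.
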